## 1.0 Objectives

Prostate cancer (PCa) is the most common invasive cancer among gay, bisexual, and other men who have sex with men (GBM), with documented disparities, yet it is severely under-researched. Because gay sex differs from vaginal sex, physiologically; the results from 614 studies focused on heterosexual men likely do not generalize to GBM with PCa. This research will advance the field in three ways: First, there have been no rehabilitation studies specific to GBM survivors of PCa, so clinicians have no relevant studies to inform best practice with their GBM patients. Second, most PCa studies have tested only one rehabilitation component. We will conduct the first study of a multi-component, biobehavioral rehabilitation program on quality of life, including both urinary and sexual function. Third, almost all PCa studies have focused on men recently treated for PCa. We will study both men recently treated (last 2 years) and men post-treatment (2+ years), using a stratified design.

The long-term objective of this research is to improve the health of GBM survivors of PCa and to provide an evidence base for rehabilitation. In Aim III, we will evaluate an online rehabilitation program tailored for GBM that addresses both the sexual and urinary effects of PCa treatment. This protocol addresses *Aim III*. “*To evaluate the effects of a structured online rehabilitation program for GBM PCa survivors*”. Note: The recruitment of participants for this study has already been reviewed and approved (see Aim II).

## 2.0 Background, Significance of Research Question/Purpose, and Existing Literature

PCa is common in GBM, and GBM have poorer outcomes than heterosexual men with PCa. However, there have been no studies to assess the effects of PCa rehabilitation in GBM, and none to assess effects of rehabilitation on gay sex. Our study premise is that structured rehabilitation, tailored for GBM with PCa, will improve their quality of life by reducing the negative sexual and urinary effects of PCa treatment. PCa is the most common non-skin cancer among men, with 180,890 new diagnoses in 2016. Three studies have examined whether sexual orientation and male partners are risk factors for PCa, but results conflict.

A recent IOM report concluded “that substantial research is needed” (p.294) to address the health disparities of LGBT persons, citing “cancer rates, risk and treatment (particularly prostate cancer among older gay and bisexual men)” [IOM’s emphasis] (p.284) as a prioritized, under-researched area. In our published literature review, we could find only 30 publications regarding GBM with PCa published this century in English, a rate of 1.9 publications per year.

There have been only 5 studies of GBM with PCa with  $n$ 's>10. The first was a qualitative study ( $N=36$ ) which concluded GBM have little-to-no understanding of the prostate, treatment or sexual sequelae. The second was a Romanian study where 12 GBM reported worse sexual outcomes following PCa treatment than 17 heterosexual men. In the third, 92 GBM reported significantly worse urinary and bowel outcomes, poorer mental health, worse quality-of-life but better sexual outcomes post-treatment than published norms. The fourth found 96 GBM had lower Gleason scores at diagnosis, and more distress at anejaculation, than 460 heterosexual men. The fifth ( $N=16$ )

## PROTOCOL TITLE: Restore: Gay Men and Prostate Cancer Aim III

concluded sexual effects of treatment are particularly “severe” for GBM. While the poor sexual outcomes demand research, the negative impact on quality-of-life adds urgency.

Sexual function is an important component of health and predictor of quality of life, including for older men. While DSM-5 defines “sexual dysfunction” as “a clinically significant disturbance in a person’s ability to respond sexually”, erectile functioning in PCa treatment is typically operationalized as “sufficient for vaginal penetration.” This gold standard is *“irrelevant for gay sex.”* Physiologically, anal penetration requires a greater degree of penile rigidity than vaginal penetration which may explain poorer sexual outcomes.

There are three main treatments for PCa. *Radical prostatectomy*, the gold standard treatment recommended by 95% of US urologists, causes urinary incontinence (UI), total semen loss, and potentially persistent erectile dysfunction (ED). For younger (<60), otherwise-healthy (heterosexual) men *with rehabilitation*, 76% report erections sufficient for vaginal sex within 3 years. GBM may be less likely than heterosexual men to choose radical prostatectomy possibly because of the sexual effects. *Radiation and cryotherapy* have long-term ED outcomes similar to or worse than radical prostatectomy, while also causing chronic rectal complications that may preclude anal sex. *Systemic treatment* involves hormonal treatments, usually in combination with surgery and radiation, with worse outcomes. *Active surveillance* is the alternative to treatment, but repeated biopsies can result in ED.

For almost all men, PCa treatment negatively impacts sexual functioning, sense of masculinity, and/or self-esteem. Erectile dysfunction (ED) and urinary incontinence (UI) are the most common sequelae of PCa treatment. Without rehabilitation, frequent UI is estimated to be 3.3-21%, and ED, 40-76% in PCa patients at 2 year post-treatment. GBM with PCa face additional challenges including the loss of the prostate as a site for sexual pleasure in receptive anal sex, persistent rectal irritation or pain sufficient to prevent receptive anal sex, loss of ejaculate (which appears more central in gay sex), and climacturia(leaking urine during orgasm) impacting oral sex. Weak erections have been hypothesized to prevent GBM with PCa from following CDC safer sex guidelines, increasing risk of HIV transmission. Some GBM adjust their role-in-sex (from insertive to receptive) to accommodate dysfunction, but this has not been well researched. PCa in GBM intersects with issues of minority status, discrimination, and stigmatization, including less familial and social support, and less partner involvement in treatment. For HIV+ GBM, HIV treatments and immune deficiency may alter the risk of PCa and cancer virulence. GBM with PCa have described post-operative sex education as “disingenuous” and “coy” because it never addresses gay sex. Challenges navigating (real or perceived) heterosexual bias in the medical setting support groups, and health systems all worsen treatment outcomes and mental health. Patient distrust of the medical community and reluctance to disclose sexuality are also barriers, with 21% of 2,560 older (50+) LGBT reporting they are not “out” to health providers and 13% reporting homophobic care. In addition, 31% of older LGBT report depression and 40% a history of suicidal ideation. Since older GBM are already at higher risk of depression and suicide, the lack of PCa treatment studies tailored for GBM is a major concern.

## PROTOCOL TITLE: Restore: Gay Men and Prostate Cancer Aim III

To ensure our structured rehabilitation program is evidence-based and state-of-the-art best practice, we conducted a systematic literature search using “prostate” and synonyms by “sexual rehabil\*” “urine”, and synonyms, since 1980, in English, French or Spanish. This yielded 614 references. We highlight three findings. First, of the 614 papers, only 127 (20.7%) focused on rehabilitation. Rehabilitation appears an under-researched area relative to treatment. Second, with few exceptions, research on rehabilitation has focused on UI or ED as separate issues and taken a component approach to studying treatment. But UI and ED often occur together; and are the top two challenges patients ask for help with, online. Combination treatment permits study of both outcomes. We conclude a structured treatment program tailored for GBM is the appropriate first (and next) step in advancing treatment for GBM with PCa.

Many PCa rehabilitation studies equate erectile functioning with vaginal sex; few studies have examined other sexual problems. For example, only two papers have examined climacturia. The first estimated 20% of otherwise continent men experience it after radical prostatectomy, and showed it increased survivors’ sexual anxiety, avoidance of sex, and low orgasmic satisfaction. The second estimated prevalence, 4-years post-treatment, to be 33.9%. No treatment studies have been published or used climacturia as a primary end point, a gap this study will address.

Of the 614 articles reviewed, 612 focused on vaginal intercourse or erections. None were in GBM. There have been no studies (in heterosexuals or GBM) of rehabilitation for insertive anal sex, receptive anal sex, and no studies to treat climacturia. This absence makes it literally impossible for clinicians to practice evidence based medicine with GBM patients. The IOM concludes this failure of science creates and sustains GBM health disparities.

As reflected in the small size of the few published studies, recruitment has been a major barrier impeding GBM with PCa research. Given our success in recruiting the largest sample to date, we are the right team to test new methods for recruitment.

### 3.0 Preliminary Data

Restore-1, our recently completed R21, is only the second NCI-funded study on GBM with PCa, and the first to reach publication. This study included two cross-sectional components: qualitative telephone interviews (n=30) and an online survey was conducted (n=193) to determine the examine the experiences of GBM with PCa and conduct a needs assessment to inform our current intervention. In qualitative interviews, men described radical prostatectomy as leaving them “humiliated,” “maimed”, “less than other gay men,” and “severely depressed.” Most (88%) GBM assessed their sexual functioning as inadequate, post-treatment resulting in poorer mental health, and decreased quality of life (QoL). Clinicians address only 3 of the 8 (38%) treatment effects commonly experienced by most GBM with PCa; leaving most GBM to treat themselves, informally. We found no evidence of any standard of care for rehabilitation, an outcome potentially explained by the lack of science to inform clinical practice. Three (2%) participants became HIV-positive after PCa treatment, raising concerns whether lack of rehabilitation led to condom difficulties and, ultimately, HIV infection. Almost all participants expressed interest in a tailored, online rehabilitation program.

## 4.0 Study Endpoints/Events/Outcomes

### 4.1 Primary Endpoint/Event/Outcome:

Health Related Quality of Life; measured as combined scores of the FACT-P and BSI-18 inventories

Sexual function and bother in anal and oral sex; measured via the EPIC-26 inventory and gay sexual functioning inventory

Urinary function and bother; measured via the EPIC-26

### 4.2 Secondary Endpoint(s)/Event(s)/Outcome(s):

Self-reported climacturia, measured via the Gay Sexual Functioning Inventory, which we are developing for this study.

## 5.0 Study Intervention(s)/Interaction(s)

### 5.1 Description:

The intervention includes six primary focus areas:

(1). *PDE5-I drugs*: Participants will be offered the option to take 60mg sildenafil orally, 3x per week for 1 year. Participants for whom it is contraindicated, who are unwilling or unable to get a prescription from their physician, who prefer to use an alternative erection enhancer not covered by our study, or do not wish to take sildenafil will still be included in the intervention.

(2). *Pelvic floor exercises (a.k.a. Kegels)*: To strengthen the levator ani muscle, both to treat UI and climacturia, videos and educational materials will demonstrate proper technique for pelvic floor exercises. For climacturia, we will emphasize voiding bladder prior to sex, shaking of the penis; and clenching pelvic floor muscles during orgasm to keep sphincters closed.

(3). *Vacuum pump and (4) masturbatory exercises*: Participants will be given a penile vacuum pump and encouraged to use it with masturbation to stimulate blood flow to the penis. In addition, they receive three different sized dildoes to help with receptive anal sex and two penile constriction rings (aka “cock rings”).

(5). *A gay man’s/couple’s guide to sex after PCa treatment*: Our mobile-enabled interactive website will have videos modeling how GBM with PCa deal with sexual challenges (e.g., disclosing PCa to a sex partner); and a male couple discussing how they have good sex, post-treatment.

(6). *Social support*: We will provide participants with a coach to help them in rehabilitation, moderated forums and other opportunities for men to exchange advice and support with peers and experts.

Participants in the intervention group will receive the following:

- PDE5-I drugs. Participants will be given a letter and instructions to obtain a prescription from their doctor. They will then obtain their drugs online or over the phone via our pharmacy partner, Marley Drug. The study will pay directly for sildenafil for all intervention participants.
- A welcome package including a vacuum pump, tension bands and anal dilators (which are recommended tools in the content), and written educational materials (which are also provided in the online intervention).

## PROTOCOL TITLE: Restore: Gay Men and Prostate Cancer Aim III

- Access to a comprehensive online intervention, including written and video educational materials on each focus area, tracking tools to encourage and measure adherence, supplemental educational materials, and moderated forums.
- Regular contact with study staff, who will encourage adherence, provide advice, and answer questions. In addition, participants will have access to monthly expert webinars, with presentations from specialists in prostate cancer and sexual health.

## 6.0 Procedures Involved

### 6.1 Study Design:

We will conduct a randomized controlled trial. Participants will be randomized 1:1 to receive either the online intervention or usual care. Treatment groups will be determined via permuted block randomization and will be stratified by relationship status and time since treatment (<2 years vs 2+years) with blocks of four.

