### 6.2 Study Procedures:

Following successful screening (see below), participants will review an online consent form which overview the study, study tasks, outlines risks and benefits, strategies to reduce risks, and risk-benefit analysis. After this, they participate in an initial telephone call from the project coordinator where they have the opportunity to ask any questions and have them answered, as well as verify information for cross-validation purposes. Then, if confirmed eligible and unique, they receive access to the baseline survey. Participants who complete the baseline survey will then be randomized, via a computer assignment, to a treatment or control group.

Participants in the control group will be notified by email. Thereafter, they will be contacted occasionally with survey links and reminders. As needed, additional casual communications will be used to increase retention.

Participants in the treatment group will be emailed immediately with a username and password to access the intervention. They will be mailed their welcome packet within one week.

Surveys will be conducted at baseline, and at 3, 6, 9, 12, 18, and 24 months follow-up. Surveys are attached.

Interaction for all participants in our study will include an online screening survey, a vetting phone conversation, an email confirmation, followed by an online baseline survey and five follow-up surveys. In addition, all participants can contact the study at any time using a 1-800 and/or our study email. In all email and phone contact, we will maintain HIPPA compliant standards to ensure no privacy violations. (e.g., we will not describe the nature of the study in phone or email messages). In addition, data will be maintained in password protected files on a secure server.

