**10.0 Study Population**

**10.1 Inclusion Criteria:**

Each participant must be:

- An adult biological male who has had sex with a man or men
- Diagnosed with PCa and treated or pending treatment, including but not limited to radical prostatectomy, radiation, and/or hormone therapy
- Recent problems with sexual and/or urinary function
- Living in the United States or its territories
- A unique, validated individual

PROTOCOL TITLE: Restore: Gay Men and Prostate Cancer Aim III

10.2 Exclusion Criteria:

- Cognitive Impairment
- Non-English speaking/reading
- Patients who underwent a bi-lateral, non nerve-sparing, prostatectomy (for which rehabilitation is not recommended as efficacious).

10.3 Screening:

Participants will complete an online screening survey to evaluate inclusion criteria (attached). Upon completion of the screener, study staff will call each participant to confirm identity, confirm screening survey answers and evaluate English and cognitive proficiency. Participants' IP addresses will be used to ensure US location and deduplication.

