## 12.0 Number of Participants

### 12.1 Number of Participants to be Consented:

We plan to recruit 450 participants: 150 participants who have undergone treatment in the past two years and 300 who have had at least two years since their PCa treatment.

We expect 80% power to detect the statistically significant differences between the intervention group and the control group. The power calculation was based on standardized effect size = 0.35, total number of observations per participant during the course of the study,  $M = 9$ , total number of participants,  $N = 450$ , assumed within-subject variability,  $\sigma^2 = 0.50$ , assumed between-subject variability,  $\tau^2 = 0.20$  and a linear change over time.

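### A single fixed block size of four leaves allocation partly predictable in a trial with no blinding described, and the plan does not say who may know the block size or earlier assignments

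*Protocol*

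**What the plan says.** **Method.** Protocol section 6.1 states: "Participants will be randomized 1:1 to receive either the online intervention or usual care". It continues: "Treatment groups will be determined via permuted block randomization", with relationship status and "time since treatment (<2 years vs 2+years) with blocks of four". One block size is given, and nothing says that it varies.

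**Sequence.** Under Protocol section 10.3, "study staff will call each participant to confirm identity, confirm screening survey answers and evaluate English and cognitive proficiency". Section 6.2 then says: "Then, if confirmed eligible and unique, they receive access to the baseline survey". Assignment comes last: "Participants who complete the baseline survey will then be randomized, via a computer assignment, to a treatment or control group". Section 17.5 adds manual checking of flagged surveys and recognises a class of response that is neither clearly valid nor clearly invalid.

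**Who learns the arm.** Control participants are told by email. Intervention participants get a login and a mailed packet (section 6.2), a coach (section 5.1) and regular staff contact. Section 23.1 places recruitment, participant communication and intervention work at one office. Section 19.1 sends quarterly reports that cover randomisation to a committee that includes study staff.

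**Silent points.** Neither document says who generates or holds the list, whether the block size is withheld from staff who vet participants, or whether those staff are kept unaware of earlier assignments.

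**The concern.** A fixed block of four with two places per arm has a known pattern. Once one arm has used its two places, the rest of the block is settled. A computer can hide the list, but it cannot hide that pattern from someone who knows the block size and has followed the assignments in a stratum.

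This matters where people use judgement at entry. Here staff assess English, cognition, uniqueness and the credibility of answers before a man is randomised. If the likely arm could be foreseen, borderline decisions could drift with it, and the arms would differ at entry. The primary outcomes are self-reported and the comparator is usual care, so participants cannot practicably be blinded. Concealment at entry is therefore one of the few protections against bias open to this trial.

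**Working it through.** The plan states no predictability figure, so there is none to reproduce.

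**Inputs**
- Block size 4, not varied, ratio 1:1, so two intervention (T) and two control (C) places per block: Protocol section 6.1.
- Sample size: "We plan to recruit 450 participants: 150 participants who have undergone treatment in the past two years", the other 300 being two or more years from treatment: Protocol section 12.1.
- Enrolment of 13 months: Protocol section 9.1.
- Assumption: the observer knows the stratum, the order and all earlier assignments in the current block.
- Assumption, used only for pace and total imbalance: two relationship levels, hence four strata. The documents do not give the number of levels.

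**Step 1. Predictability just before assignment.** There are six possible blocks and 6 × 4 = 24 positions. In TTCC and CCTT, positions 3 and 4 are determined (2 × 2 = 4). In the other four blocks only position 4 is (4 × 1 = 4).
- Determined: 8/24 = 33.3%. By position: 0, 0, 1/3, 1.
- Best guess (choose the arm that is behind): (1/2 + 2/3 + 2/3 + 1)/4 = 17/24 = 70.8%, against 50% with no predictability.
- Over 450 men in complete blocks: 450/3 = 150 determined allocations. Incomplete last blocks lower this slightly. A stratum of 75 has 18 full blocks and three further places: (18 × 4/3 + 1/3)/75 = 24.33/75 = 32.4%.

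**Step 2. Predictability at the vetting call.** The man vetted now takes a later place if others in his stratum are randomised before he finishes the baseline survey. Average over a block with 0, 1, 2 or 3 places already filled, and let the observer know exactly how many men intervene.

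| Men randomised in between | Certain | Best guess |
|---|---|---|
| 0 | 1/3 = 33.3% | 17/24 = 70.8% |
| 1 | (0 + 0 + 1/3 + 0)/4 = 8.3% | (1/2 + 2/3 + 2/3 + 1/2)/4 = 58.3% |
| 2 | 0% | (1/2 + 2/3 + 1/2 + 1/2)/4 = 54.2% |
| 3 or more | 0% | 50% |

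With one man in between, certainty arises only when two places are filled and both went to the same arm, which has probability 1/3.

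**Step 3. How many men intervene?** The lag from call to completed survey is not stated. The planned pace is 450/13 ≈ 35 a month. Spread over four equal strata, that is about two per stratum per week. If the number intervening is Poisson with mean m, certainty is e^(−m)(1/3 + m/12):
- m = 0.5: 0.607 × 0.375 = 23%
- m = 1: 0.368 × 0.417 = 15%
- m = 2: 0.135 × 0.500 = 7%

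**Step 4. Varying the block size.** Sequences of 75 and of 112 men per stratum were simulated (3,000 each). The observer knew the possible sizes but not their order, and guessed by updating probabilities after each assignment. As in step 1, the figures apply just before assignment.

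| Blocks | Certain | Best guess |
|---|---|---|
| Fixed 4 | 33.3% | 70.8% |
| Fixed 6, known | 25% | 68.3% |
| Fixed 8, known | 20% | 66.6% |
| Random 4 and 6 | about 5.5% | about 69% |
| Random 4, 6 and 8 | about 2% | about 68% |

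Varying the size removes most of the certainty but little of the guessing advantage.

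**The case against.** The strongest reply is about timing. Staff judgement is exercised at the call, while assignment is by computer after a survey that the participant completes in his own time. Staff do not choose his slot, and men vetted in one order may be randomised in another. This stands: one third is an upper limit at the point where discretion is used, and step 2 shows how quickly it falls. A reader might infer that a third of allocations are known when eligibility is decided. The documents do not support that.

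A second reply is about knowledge. A reader might infer that one team both vets and coaches and so knows the running sequence in each stratum. Section 6.2 gives the call to the project coordinator, section 10.3 to study staff, and section 5.1 mentions a coach. Only a shared office is documented, and the screener, from which the stratum might be read, is an attachment not shown. This also stands, but it works both ways, since nothing separates the roles either.

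Third, a reader might infer that selection at entry could never be detected. That goes too far. Every man completes a baseline survey before randomisation, so the arms can be compared, and Protocol section 17.3 allows adjustment for treatment time, relationship status, comorbidities and demographics. What remains out of reach is selection on something not measured.

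Finally, varying the block size moves the best guess only from 71% to 68%. That is correct, and it is why the remedy cannot rest on block size alone.

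**Conclusion.** The point holds as an inexpensive improvement to the design. A fixed block of four makes 33% of allocations certain, and a best guess right 71% of the time, just before assignment. This applies only to someone who knows the stratum, the order and all earlier assignments in the block. At the vetting call, certainty is about 8% with one intervening randomisation in the stratum and nil with two or more.

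The one-third figure is exact for complete blocks and does not depend on the number of strata. That the trial is open is inferred from the usual-care comparator and the staff contact in one arm, since the documents describe no blinding. Whether vetting staff could in practice predict anything depends on access that the documents leave unstated. The finding is an avoidable vulnerability. Nothing in the documents shows that allocation was foreseen or that bias occurred.

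**What to change.** **If randomisation is still open**
- Use permuted blocks of randomly varying size (for example 4, 6 and 8) within the same strata.
- Withhold the block sizes and earlier assignments from staff who vet participants, and take the sizes out of the documents those staff use.
- Have the list generated and held by someone already on the team who neither vets nor coaches, and name that role in section 6.1.

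**Cost.** A setting in the randomisation program, a few sentences of text and a separation of duties. Within-stratum imbalance can reach 4 instead of 2 at any time. If all four assumed strata ended at that limit in the same direction, the arms would differ by 16 of 450, for a loss of efficiency of (16/450)² = 0.13%, which is trivial.

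**If enrolment has closed.** This is likely, since section 9.1 planned enrolment to February 2020 and the SAP is dated November 2023. Report which roles had access to the block size and to earlier assignments during recruitment, and present baseline comparisons by arm within stratum. State that these comparisons can show measured imbalance but cannot exclude unmeasured selection. The cost is a paragraph and a table from data already collected.
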